6.3 Other Variables

The following variables will be derived for analysis:

- The duration of exposure in treatment period

For each subject, the Length of Time on study drug in treatment period will be calculated in days, using the following formula:

(‘Date of Last Study Drug Taken in Treatment period’[#] - ‘Date of First Study Drug Taken in Treatment period’[#]) + 1

#: These dates can be taken from [Date of Study Drug Taken-page of the Case Report Form]

- The duration of the primary diagnosis (unit: months)

Duration of the primary diagnosis (months) = 12 * (year of visit date of screening visit (Visit 1) – year of Diagnosis) + month of visit date of screening visit (Visit 1) – month of Diagnosis.

If the month for diagnosis is missing, then the month will be imputed by January. As a result, if the duration of primary diagnosis is less than 1 month, then it will be assumed to be 1 month.

If the month and year for diagnosis is missing, then duration of the primary diagnosis is missing.

- Percent overall compliance of the study drug (Mirabegron/Placebo) and Tamsulosin during treatment period

Overall compliance to the dosing schedule will be examined for subjects whose total tablet count of the study drug (Mirabegron/Placebo) and Tamsulosin is known.

Number of tablets which should have been taken depends on the duration of exposure because they should be taken as 1 tablet once daily after breakfast. The following formula can be used for both study drug (Mirabegron/Placebo) and Tamsulosin:

$$\frac{[\text{Total number of tablets consumed during treatment period}]}{[\text{The duration of exposure in treatment period}]} \times 100$$

Where, total number of tablets consumed will be calculated as:

(total number of tablets dispensed) – (total number of tablets returned) – (total number of tablets lost).

- Previous and concomitant medication

Previous medication is defined as medication with at least one dose taken before the date of the first dose of study drug in treatment period.

Concomitant medication is defined as medication with at least one dose taken between the date of first dose (inclusive) and the date of last dose (inclusive) of study drug in treatment period.

7 STATISTICAL METHODOLOGY

7.1 General Considerations

Assessment at Visit 2 (Day 1) will be treated as baseline for efficacy and safety analysis.

The End of Treatment assessment is defined as the last post-Baseline assessment during the double-blind study period for which the primary efficacy data are available.

For continuous variables, descriptive statistics will include the number of subjects (n), mean, standard deviation, minimum, Q1 (25th percentile), median, Q3 (75th percentile) and maximum. Frequencies and percentages will be displayed for categorical data. Percentages by categories will be based on the number of subjects with no missing data, i.e. will add up to 100%.

Summaries based on FAS and PPS (e.g. disposition, baseline and efficacy data) will be presented by planned treatment group, unless specifically stated otherwise. Safety analysis and other summaries based on SAF will be presented by actual treatment received.

All statistical comparisons will be made using two sided tests at the $\alpha=0.05$ significance level unless specifically stated otherwise. All null hypotheses will be of no treatment difference, all alternative hypotheses will be two-sided, unless specifically stated otherwise.

All data processing, summarization, and analyses will be performed using Windows SAS[®] Version 9.4. Specifications for table, figures, and data listing formats can be found in the Tables, Listings and Figures (TLF) specifications for this study.

For the definition of subgroups of interest please refer to section [7.8](#)

Total and subscale score of OABSS, IPSS and OAB-q are as follows:

Name of score	Subscale score	Calculation	Range
IPSS (Question 1-7 and Quality Life Item)	Storage Subscale	Sum of Question 2,4 and 7	0-15
	Voiding Subscale-1	Sum of Question 3, 5 and 6	0-15
	Voiding Subscale-2	Sum of Question 1, 3, 5 and 6	0-20
	Quality of Life Item	-	0-6
	Total Index Score	Sum of Question 1 to 7	0-35
OABSS (Question 1-4)	Daytime frequency	Question 1	0-2
	Nighttime frequency	Question 2	0-3
	Urgency	Question 3	0-5
	Urgency incontinence	Question 4	0-5
	Total Score	Sum of Question 1 to 4	0-15
OAB-q (Question 1-33)	Symptom bother	Sum of Q1-8	0-100
	Coping	Sum of Q9,11,16,21,22,26,32,33	0-100
	Concern	Sum of Q12,13,14,19,23,25,29	0-100
	Sleep	Sum of Q10,15,17,24,30	0-100
	Social Interaction	Sum of Q18,20,27,28,31	0-100
	Total Health-Related Quality of Life scores	Sum of OAB-q subscale scores (Coping, Concern, Sleep, Social Interaction)t	0-100

The coding dictionary ‘World Health Organization Drug Dictionary (WHO-DD) Enhanced (December 1, 2015)’ and ATC classification will be used for previous and concomitant medication. And the coding dictionary ‘MedDRA (ver.18.1)’ will be used for name of disease (Adverse Event, medical history etc.).

7.2 Study Population

7.2.1 Disposition of Subjects

The following subject data will be presented:

- Number of subjects with informed consent, discontinued before randomization and randomized (overall only);
- Number and percentage of subjects discontinued before screening period by primary reason (overall only);
- Number and percentage of subjects discontinued in screening period by primary reason (overall only);

Screening failure is all subjects who signed informed consent but discontinued before randomization.

- Number and percentage of subjects randomized in each analysis set, by treatment group and overall;
- Number and percentage of subjects who completed or discontinued the study, by primary reason for study discontinuation for randomized subjects and by treatment group; and
- Number and percentage of subjects excluded from PPS by reason for exclusion defined in section [5.2.1](#) by treatment group for FAS.

7.2.2 Protocol Deviations

Protocol deviations as defined in the study protocol (Section 8.1.6 Protocol Deviations (*Unique to Korea*)) will be assessed for all randomized subjects. The number and percentage of subjects meeting any criteria will be summarized for each criterion and overall, by treatment group and total as well as by study site. Subjects deviating from a criterion more than once will be counted once for the corresponding criterion. Any subjects who have more than one protocol deviation will be counted once in the overall summary. A data listing will be provided by site and subject.

The protocol deviation (PD) criteria will be uniquely identified in the summary table and listing. The unique identifiers will be as follows:

PD1 - Screening examination was performed before informed consent.

PD2 - Did not obtain updated informed consent from.

PD3 - No efficacy data after administration

PD4 - Violate the inclusion Criteria or exclusion criteria assessed at Visit 1 (Screening)

PD5 - Violate the inclusion Criteria or exclusion criteria assessed at Visit 2 (Baseline)

PD6 - Drug compliance during the Screening period and Treatment period of less than 80%

PD7- Duration of fixed dose period administration was less than 42 days

PD8 - Lack of diary entries at Visit 2 or the last visit during the Treatment period

PD9 - Receive of the prohibited concomitant medications/therapies

PD10 - Antihistamines, ephedrine hydrochloride, and methylephedrine hydrochloride for common cold, etc.

PD11-Lack of diary entries during go out

7.2.3 Demographic and Other Baseline Characteristics

Demographic and other baseline characteristics will be summarized by descriptive statistics by treatment group for the SAF, FAS and PPS.

Number and percentage of subjects in each country will be presented by treatment group for the SAF, FAS and PPS.

Descriptive statistics for age, duration of the primary diagnosis, body weight, body mass index (BMI), height, prostate volume, PSA and QT interval, corrected for heart rate according to Fridericia's formula (QTcF interval), IPSS (total/, QOL,), OABSS-total, OAB-q (Symptom Bother, total), Qmax, Qave, PVR at visit 1 will be presented. Also, IPSS (total/, QOL,), OABSS-total, OAB-q (Symptom Bother, total), Qmax, Qave, PVR, Micturition diary(Micturitions, Urgency, Urgency Incontinence, Incontinence, Volume voided per Micturitions, Nocturia) at visit 2 will be presented. Frequency tabulations for sex, race, ethnicity, age group (defined in section 7.8) medical condition of primary diagnosis, status of urinary incontinence, duration of the primary diagnosis group (defined in section 7.8). This will be done for the SAF, FAS and PPS by treatment group. Additionally, to detect the difference of distribution between treatment groups, 2-sample t-test will be used for numerical data and Fisher's exact test will be used for categorical data (Two-sided significance level of 0.05 will be used as a measure).

Complication is coded in MedDRA, and will be summarized by System Organ Class (SOC) and Preferred Term (PT), by treatment group for the SAF, FAS and PPS. The definition of complication is all medical history that is ongoing at Visit 1.

7.2.4 Previous and Concomitant Medications

Previous and concomitant medications are coded with WHO-DD, and will be summarized by therapeutic subgroup (ATC 2nd level) and chemical subgroup (ATC 4th level) and preferred WHO name by treatment group for the SAF, FAS and PPS.

As with previous medication, concomitant medication will be summarized for each treatment group by therapeutic subgroup (ATC 2nd level) and chemical subgroup (ATC 4th level) and preferred WHO name for the SAF, FAS and PPS. Subjects taking the same medication multiple times will be counted once per medication. A medication which can be classified into several chemical and/or therapeutic subgroups is presented in all chemical and therapeutic subgroups.

If the start day of concomitant medications/therapy is missing, then the day will be imputed by 1st of the months. As a result, if the start day of concomitant medications/therapy is earlier than the first administration date of the study drug for treatment period, then the onset date will be re-imputed by the same date as the first administration date of the study drug for treatment period. If the end day of concomitant medications/therapy is missing, then the day will be imputed by last of the months. As a result, if the end date of concomitant medications/therapy is earlier than the first

administration date of the study drug for treatment period, the end date will be re-imputed by the same date as the first administration date of the study drug for treatment period.

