5.1.3.2 Concomitant Treatment

Drug classes and specific medications that are prohibited during the study are provided in Appendix 12.1 List of Excluded Concomitant Medications.

All concomitant medications and non-medication therapies received by a subject from Baseline to the end of the Treatment period will be entered on the eCRF, as described below:

Concomitant treatment	Investigation period	Data to be entered on the eCRF
Concomitant medication (all drugs)	From Visit 1 to the end of the Treatment period	Drug name, route of administration, administration period, reason for use
Concomitant therapy (all non-medication therapies)		Therapy name, treatment period, reason for use

The excluded concomitant medications (defined in Appendix 12.1) can be allowed to use under the conditions below:

- 1) From the day following the dispensing of the study drug for the Screening period to the end of the Treatment period, none of the prohibited concomitant medications listed in Appendix 12.1 should be concomitantly used. However, the following drugs may be concomitantly used:
 - Eye drops
 - Transdermal formulations, excluding β -agonists and drugs for the treatment of urinary storage and voiding dysfunction
 - Nasal drops, excluding drugs for diabetes insipidus
 - Topical agents
 - Inhaled β -agonists used to relieve acute symptoms such as bronchial asthma
 - Chinese herbal medicines used for the treatment of conditions other than urinary storage and voiding dysfunction
- 2) The following drugs may be used concomitantly for a short period of time (i.e., up to a total of 5 days during the interval from the day following a visit to the next visit), except during the micturition diary period:
 - Parasympathetic inhibitors/parasympatholytic drugs for peptic ulcer, etc.
 - Antihistamines, ephedrine hydrochloride, and methylephedrine hydrochloride for common cold, etc.
- 3) Transient concomitant use of parasympathetic inhibitors/parasympatholytic drugs will be allowed, if used in preparation for an examination, except during the micturition diary period.
- 4) Concomitant use of 5α -reductase inhibitors will be allowed (the dosage shall not be changed for study period), if the subject has been on treatment for a year or more.
- 5) Transient concomitant use of PDE5 inhibitor for ED treatment will be allowed, except during the micturition diary period.

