7.5.1 Adverse Events

Following definitions of AE will be used for analysis.

As for definition of TEAE and drug-related adverse events, refer to section [6.2](#)

“Adverse event leading to permanent discontinuation of study drug” are events selected “DRUG WITHDRAWN” checkbox as both or either one of “Action Taken for Study Drug (Mirabegron/Placebo)” and “Action Taken for Study Drug (Tamsulosin)”.

“Death” is event checked “Death” checkbox as detail of serious adverse event.

If the onset day TEAE is missing, then the day will be imputed by 1st of the months. As a result, if the onset date of TEAE is earlier than the first administration date of the study drug for treatment period, then the onset date will be re-imputed by the same date as the first administration date of the study drug for treatment period. If the end date TEAE is missing, then the date will be imputed by last day of the giving months. And if, the month TEAE is missing, then the date will be imputed by 31DEC. As a result, if the end date of TEAE is earlier than the first administration date of the study drug for treatment period, then the onset date will be re-imputed by the same date as the first administration date of the study drug for treatment period. The imputed onset day and end day will be used for summary of AE with time interval (section 7.5.1.4).

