7.5.1.5 Onset/Prevalence/First Onset of AE (Time Intervals)

The number and percentage of subjects with TEAEs, as classified by SOC and PT will be summarized in the following categories for each treatment group by time interval.

- Onset of AE: For each adverse event in a particular interval, a subject will be counted if there is an onset of a treatment-emergent adverse event regardless of onset in other intervals.
- Prevalence of AE: For each adverse event in a particular interval, a subject will be counted if the adverse event started, continued, or stopped during that interval.
- First Onset of AE: For each adverse event only the earliest onset will be counted if there is more than one onset of that adverse event.

Time intervals will be categorized according to the following categories:

- less than 14 days;
- at least 14 days, less than 28 days;
- at least 28 days, less than 56 days;
- at least 56 days, less than 84 days; and
- 84 days or more.

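### SAP 7.2.4 moves a partial medication end date to first double-blind dose only when the recorded month shows the drug had already stopped; the AE onset reset in SAP 7.5.1 also lacks a month check

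*SAP*

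**What the plan says.** **Medications.** SAP 7.2.4 fills a missing end day with the last day of the recorded month. If the result precedes first double-blind dose, "the end date will be re-imputed by the same date as the first administration date of the study drug for treatment period". A missing start day becomes the first of the month and is also moved to first dose "if the start day of concomitant medications/therapy is earlier than the first administration date of the study drug for treatment period". Neither reset looks at the recorded month.

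SAP 6.3 defines a concomitant medication as "medication with at least one dose taken between the date of first dose (inclusive) and the date of last dose", both dates inclusive. The table in protocol 5.1.3.2 collects concomitant medication "From Visit 1 to the end of the Treatment period", so drugs used only during Screening are in the data.

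**Adverse events.** SAP 7.5.1 fills a missing onset day with the first of the month and moves it to first dose "if the onset date of TEAE is earlier than the first administration date of the study drug for treatment period". The next rule reads "if the end date of TEAE is earlier than the first administration date of the study drug for treatment period, then the onset date" is reset: the trigger is the end date, but the date changed is the onset. The section then names one use: "The imputed onset day and end day will be used for summary of AE with time interval (section 7.5.1.4". Section 7.5.1.4 is Relationship of AE; the interval analysis is 7.5.1.5, "Onset/Prevalence/First Onset of AE (Time Intervals".

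SAP 7.10.1 gives imputed dates a wider role, which includes deciding whether an AE is treatment emergent. Protocol 5.5.1.1 does not count an AE that began in Screening as a TEAE unless it worsened during double-blind treatment.

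**The concern.** Moving an uncertain date to first dose is a reasonable conservative rule when the event might have fallen on either side of that date. It is not reasonable when the recorded month already settles the question. The 7.2.4 end-date clause works only in that second situation. The 7.5.1 onset reset works in both and does not separate them.

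At stake are the concomitant-medication tables, the AE time-interval tables and, if 7.10.1 governs, the TEAE counts. A drug or event known to belong to Screening could be reported as belonging to double-blind treatment.

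**Working it through.** The plan gives no figure for these rules, so there is none to reproduce. The check is of date logic.

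**1. When the end-date clause acts.** Let F be the first-dose date, M the recorded stop month, and E the last day of M.

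- M later than the month of F: E is after F, no reset.
- M the same month as F: E is on or after F, because the last day of a month cannot precede any day in it. No reset.
- M earlier than the month of F: E is before F, so the date is reset.

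The clause therefore acts if and only if M is earlier. The true stop date is then no later than E, hence before F. As a check, all 366 first-dose dates of 2016 were crossed with true stop dates from 120 days before to 120 days after first dose (366 × 241 = 88,206 pairs). There were 0 resets with a true stop on or after first dose, and 0 disagreements with the month rule.

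**2. Example, first dose 10 March 2016.**

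| Recorded end | Imputed end | Final end under 7.2.4 | Meets 6.3 by final date? | Final end without the clause |
|---|---|---|---|---|
| ??-Feb-2016 | 29 Feb | 10 Mar | Yes | 29 Feb, not concomitant |
| ??-Mar-2016 | 31 Mar | 31 Mar | Yes | 31 Mar, concomitant |

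The February drug had stopped at least 10 days before first dose. It qualifies only because it was given the first-dose date, which 6.3 includes.

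**3. How often, among affected records.** Assume the true stop date is uniform over Screening, with first dose on each day of 2016. Screening is 28 days nominally, and 21 to 35 by the Visit 1 window. The base is screening-only drugs with a missing end day.

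| Screening | Pairs (366 × days) | Reset by the clause | Final date meets 6.3, with clause | Final date meets 6.3, clause deleted |
|---|---|---|---|---|
| 21 days | 7,686 | 36.1% | 100% | 63.9% |
| 28 days | 10,248 | 47.5% | 100% | 52.5% |
| 35 days | 12,810 | 57.8% | 100% | 42.2% |

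The last column is 100% minus the reset share. Those drugs have a stop month equal to the first-dose month, so overlap cannot be excluded. These are shares of partial-date records, not of all medications.

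**4. AE onset.** Under the same assumption, every screening AE with a missing onset day is moved to first dose. In 47.5% of them (36.1% to 57.8%) the recorded month lies wholly before the first-dose month, so the onset was known to be pre-treatment. With first dose 10 March 2016, an onset of ??-Feb-2016 becomes 1 February and then 10 March.

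**5. What the moved onset is used for.** Under 7.5.1 alone, it feeds the interval summary and falls in the shortest interval, under 14 days. Under 7.10.1 it also decides TEAE status, and the February event becomes a TEAE without having worsened, against protocol 5.5.1.1. The two SAP sections do not agree on the use.

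**6. Whether the onset check box stops this.** SAP 6.2 uses the box for events on Day 1, which SAP 7.10.3 defines as the day of prescription. If first dose is on Day 1 and the box is marked as onset before first dose, the event is kept out. If first dose is the day after dispensing, as protocol 5.1.5 instructs, the moved onset is not on Day 1 and the box does not apply.

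**The case against.** **7.2.4 may cover only drugs already classed as concomitant.** The clause is worded for concomitant medications, and no sentence says outright that imputed dates decide that status; 7.10.1 speaks of allocating concomitant medication to a treatment group. This stands to the extent that the drug *can* be tabulated as concomitant, rather than certainly will be. It does not rescue the clause, which on that reading has no valid case to act on. Protocol 5.1.3.2 also uses the word for all drugs from Visit 1.

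**7.5.1 is the more specific text and limits the use to interval tables.** That is a fair reading, so the effect on TEAE counts is conditional on 7.10.1. The sections still need to be reconciled.

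**The data specification document cited in SAP 7.10 may hold a month check.** It may; it is not available here. If so, it and the SAP text differ and should be aligned.

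A reader might infer three stronger points that the documents do not support:

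- *That a moved onset always escapes the check box by falling on Day 2.* The protocol's definition of the Screening period and its section 7.5.2 place dosing at Visit 2, and the box itself presupposes that first dose can be on Day 1.
- *That the 7.5.1 end-date sentence is meant to overwrite complete onset dates.* The sentence is worded for TEAEs, and the parallel sentence in 7.2.4 resets the end date. A slip of onset for end is the likelier explanation.
- *That the medication start reset distorts the tables by giving starts after recorded ends.* Medications are tabulated by class and name, and a complete end date before first dose already keeps a drug out of the concomitant group.

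**Conclusion.** The point holds as a minor one. The 7.2.4 end-date clause acts only against records showing that the drug had stopped; this follows from the calendar and needs no assumption about the data. The 7.5.1 onset reset is defensible when the recorded month is the first-dose month and wrong when it is earlier. Its effect on TEAE counts depends on 7.10.1 being followed and, for subjects first dosed on Day 1, on the check box. The end-date wording and the 7.5.1.4 citation are corrections of text.

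The effect on counts is unknown, because the number of partial dates is not given. The percentages above rest on uniform stop or onset dates over Screening and describe partial-date records only. Exposure is limited to the concomitant-medication tables, the AE interval tables and possibly the TEAE counts. The primary analysis is unaffected, and listings keep the actual partial dates, so moved records can be traced. A reader might infer a bias between arms; the documents give no ground for it, since Screening precedes randomization and misplaced records should fall about equally on both.

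**What to change.** Before unblinding:

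- **(a)** Delete the end-date re-imputation clause in 7.2.4. Drugs whose stop month is the first-dose month will still count as concomitant, which is the conservative choice because overlap cannot be excluded.
- **(b)** Reset a partial medication start or AE onset to first dose only when its recorded month and year are those of first dose (or the month is unknown and the year is the same) and no known end date precedes first dose. Otherwise keep it in its recorded month or year.
- **(c)** Make the 7.5.1 end-date sentence act on the end date, without moving it past its recorded month, and change the cross-reference to 7.5.1.5.
- **(d)** Reconcile 7.5.1 with 7.10.1 so that imputation cannot make a TEAE of an AE whose recorded month or year precedes first dose.
- **(e)** Align the data specification document.

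The cost is a few lines of SAP text and derivation code. No new data are needed; in particular, the change does not rely on the onset check box beyond its Day 1 use, since the documents do not show that it is collected otherwise.
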